- Trial treatment should be administered on Day 1, Day 8 and Day 15 of each cycle of 28 days. Interruptions from the treatment plan may be allowed for toxicity management, but require consultation between the investigator and Sponsor, and written documentation of the collaborative decision on subject management.
- All trial treatments will be administered on an outpatient basis.
- **Romidepsin should be infused over 4 hours.** Sites should make every effort to target infusion timing to be as close to 4 hours as possible. However, given the variability of infusion pumps from site to site, a window of -5 minutes and +10 minutes is permitted.
- Romidepsin must be stored as per prescribing information. .
- Prescribing information should be referred for specific instructions for Romidepsin reconstitution, preparation of the infusion fluid, and administration.

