C1D1	All PK matched time points (Pre-infusion (0), 1, 2, 3, 5, 7, 9, 10 hrs).	Time points are with respect to Romidepsin infusion.
C1D8	All PK matched time points (Pre-dose (0), 0.5, 1 (pre-infusion of Romidepsin), 2, 3, 4, 6, 8, 10, 11 hrs post-dose).	Time points are with respect to Tenalisib dosing
C1D15	Before-infusion and immediately after infusion.	Time points are with respect to Romidepsin infusion.
Rest of the cycles (Day 1 of each cycle)	Before-infusion and immediately after infusion.	Time points are with respect to Romidepsin infusion.

Dose Expansion		
Days	Time points	Note
Screening	Within last 28 days	-
Day 1 of each cycle	Before Romidepsin infusion.	

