8. Chemistry Panel I must be done \leq 7 days prior to C1D1. However, if these initial examinations are obtained within 72 hours of C1D1; they do not have to be repeated. These tests will be performed at supplementary (unscheduled) visits if clinically indicated.
9. Chemistry Panel II must be done \leq 7 days prior to C1D1. However, if these initial examinations are obtained within 72 hours of C1D1; they do not have to be repeated. During treatment, the labs will be performed at C3D1 (\pm 1 days), C5D1 (\pm 1 days) and C8D1 (\pm 7 days) and/ or at the EOT. These tests will be performed at supplementary (unscheduled) visits if clinically indicated.
10. Serology includes HIV, HBV, HCV and CMV. Historical evidence in last 12 weeks is acceptable.
11. PT/INR: PT and INR test must be done \leq 7 days prior to C1D1. However, if initial examination is obtained within 72 hours of C1D1; this do not have to be repeated. In case of abnormality, additional tests including aPTT to be done as per investigator discretion. This test will be performed at supplementary visits if clinically indicated.
12. Pregnancy test is required for women of child bearing potential. A serum/urine pregnancy test will be performed at screening and C1D1 (within 72 hours) of dosing. Urine pregnancy test will be performed at other visits as indicated.
13. 12-lead ECG: PK matching ECG will be done on C1D1 and C1D8. Please refer ECG table for detailed time points. Additional ECGs will be obtained if clinically indicated. Triplicate ECGs will be performed to confirm the significant changes of single ECG. Refer Section 6.5.
14. PK: The blood will be collected for PK on following time points: C1D1: Pre-infusion (0), 1, 2, 3, 5, 7, 9, 10 hrs post-infusion. C1D8: Sampling with respect to Tenalisib dosing. Pre-dose (0), 0.5, 1, 2, 3, 4, 5, 6, 8, 10, 11 post-dose. Pre-dose sample will be taken on C2D1, C3D1 and C4D1. Patient will be hospitalized on C1D1 and C1D8 at the discretion of the site in order to facilitate multiple procedures (e.g. PK blood draws, ECGs) that required to be performed on C1D1 and C1D8. On C2D1, C3D1, C4D1, patients should consume their morning dose at the clinic after the pre-dose sample. Refer Section 6.10.

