15. A bone marrow biopsy: PTCL: Bone marrow biopsy should be collected \leq 12 weeks prior to C1D1 and/or to confirm a complete response to the study drug. If patient has negative bone marrow at baseline, there is no need to have it repeated to confirm CR. Additional biopsy will be obtained if clinically indicated. CTCL patients with predominantly blood involvement (B₂) will have a bone marrow biopsy at screening (unless it has been shown to be negative within the last 6 months) and as indicated to confirm a complete response.
16. Skin biopsy: In CTCL patients, skin biopsy should be performed at screening, and to confirm a complete response. Historical data of 12 weeks is acceptable.
17. Radiological scan: In PTCL and CTCL patients with nodal and visceral involvement, PET and “diagnostic quality” CT scan will be performed at the time of screening within 28 days of screening. Following screening, CT scans should be repeated at C3D1 (\pm 7 days), C5D1 (\pm 7 days) and C8D1 (\pm 7 days). PET should be done at C3D1 (\pm 7 days) and to confirm CR.
18. Skin assessment: In all CTCL patients, mSWAT will be performed at the time of screening within 28 days of screening and at C3D1 (\pm 7 days), C5D1 (\pm 7 days) and C8D1 (\pm 7 days). Disease response assessment will be performed at C3D1 (\pm 7 days), C5D1 (\pm 7 days) and C8D1 (\pm 7 days) and/ or at the EOT or as clinically indicated using mSWAT.
19. Skin photograph: In CTCL patients, skin lesion photograph will be taken at screening, at the time of response (PR/CR/PD) and at other time points as required by the PI.
20. Blood will be collected for biomarkers (e.g. sIL2R and CTACK for PTCL; CD30, IL-31 and IL-32 for CTCL).
21. Tenalisib will be administered orally twice a day from Day 3 (C1D3) onward in 28-days of cycle for 7 cycles in absence of disease progression or toxicity warranting discontinuation of therapy. On the day of Romidepsin administration, the morning dose of Tenalisib should be given in clinic one hour prior to Romidepsin infusion. Tenalisib will be dispensed at the start of each cycle (C1D1, C2D1, C3D1 ...). Only in Cycle 1, Tenalisib will be

given starting from Day 3 (i.e. C1D3). Patients will be, therefore, be instructed to start the treatment on C1D3 and will be informed that they will receive Tenalisib for 25 days in the first cycle.

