- 22. Romidepsin will be administered as an intravenous infusion over 4 hours unless progression of disease or toxicity warranting discontinuation of therapy.
- 23. All AEs regardless of seriousness or relationship to study drug should be recorded spanning from the informed consent drug until 30 calendar days after the last dose of study drug.
- 24. Post C8D1, *patient experiencing clinical benefit* with no evident disease progression will be given the opportunity to enroll in an open-label compassionate use study protocol and will be followed up. Excluding patients who participate in compassionate use study protocol, all other patients will undergo the end-of-treatment (EOT) assessments within 7days after the last dose of study drug or discontinuation from the study.
- 25. Patients should be followed for AEs for 30 calendar days after the last dose of study treatment. Telephonic follow up during this period is acceptable. All new AEs occurring during this period should be reported and followed until resolution unless, in the opinion of the investigator, the adverse event or laboratory abnormality/ies are not likely to improve because of the underlying disease.

Table 6: Schedule of Events for Dose Expansion

	Screening	C1				C2				C3			C4-C7			EOT ²² /C8D1	EOS ²³
Day	D-28 to 0	D1	D8	D15	D22	D1	D8	D15	D22	D1	D8	D15	D1	D8	D15	D1	
Window period	-28	0	±1	±1	±1	±1	±1	±1	±1	±1	±1	±1	±1	±1	±1	+7	+30
Study Days	D-28 to 0	1	8	15	22	29	36	43	50	57	64	71	-	-	-	197	227
Informed Consent ¹	X	-	-	-		-	-	-	-	-	-	-	-	-	-	-	-
Demographics ²	X	-	-	-		-	-	-	-	-	-	-	-	-	-	-	-
Medical history ³	X	-	-	-		-	-	-	-	-	-	-	-	-	-	-	-
Vitals ⁴	X	X	X	X	X	X	X	X	X	X	X	X	X	X	X	X	-
Height and weight ⁵	X	X	X	X	X	X	X	X	X	X	X	X	X	X	X	X	-
Complete Physical exam ⁶	X	-	-	-	-	-	-	-	-	-	-	-	-	-	-	X	-
Abbreviated Physical exam ⁶	-	X	X	X		X	X	X		X	X	X	X	X	X	-	-
ECOG Performance Status	X	X	-	-	-	-	-	-	-	X	-	-	-	-	-	X	-
Tumor staging	X	-	-	-	-	-	-	-	-	-	-	-	-	-	-	-	-
Laboratory assessment																	
Complete blood count ⁷	X	X	X	X	X	X	X	X	X	X	X	X	X	X	X	X	-
Chemistry panel I ⁸	X	X	X	X	X	X	X	X	X	X	X	X	X	X	X	X	-
Chemistry panel II ⁹	X	X	-	-	-	-	-	-	-	X	-	-	X	-	-	X	-
Serology ¹⁰	X	-	-	-	-	-	-	-	-	-	-	-	-	-	-	-	-
PT and INR ¹¹	X	X	X	X	X	X	X	X	X	X	X	X	X	X	X	X	-
Urinalysis (routine)	X	X		X		X	-	X		X		X	X		X	X	-
Pregnancy test ¹²	X	X	-	-	-	X	-	-	-	X	-	-	X	-	-	X	-
12-lead ECGs ¹³	X	X	-	-	-	X	-	-	-	X	-	-	X	-	-	X	-
Bone marrow biopsy ¹⁴	X	-	-	-	-	-	-	-	-	-	-	-	-	-	-	-	-

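### No C1D1 schedule samples romidepsin at the end of its 4 h infusion, and only footnote 14 has that draw on C1D8, so Cmax for romidepsin alone is understated and the two days may not be comparable.

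*Protocol*

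**What the plan says.** Protocol 3.1.2 makes Cmax and tmax of both drugs secondary PK endpoints. Section 3.4.3.2 states "Romidepsin should be infused over 4 hours", and Table 5 footnote 21 that "the morning dose of Tenalisib should be given in clinic one hour prior to Romidepsin infusion".

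The PK sampling times appear in three places:

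- **Table 5 footnote 14.** For C1D1: "Pre-infusion (0), 1, 2, 3, 5, 7, 9, 10 hrs post-infusion". For C1D8: "C1D8: Sampling with respect to Tenalisib dosing", with times "Pre-dose (0), 0.5, 1, 2, 3, 4, 5, 6, 8, 10, 11 post-dose". It does not say which drug the 5 h sample is assayed for, and it refers the reader to Section 6.10.
- **Section 6.5 (ECGs matched to PK).** C1D1 has the same hours as footnote 14. C1D8 reads "0.5, 1 (pre-infusion of Romidepsin), 2, 3, 4, 6, 8, 10, 11 hrs post-dose" after a pre-dose point, with no 5 h point.
- **Section 6.10 (PK table).** The romidepsin columns read pre-infusion, 1, 2, 3, 5, 7, 9, 10 h. The C1D8 Tenalisib column reads 0, 0.5, 1, 2, 3, 4, 6, 8, 10, 11 h. Romidepsin pre-infusion sits beside Tenalisib 1 h, and romidepsin 1 h beside Tenalisib 2 h, so romidepsin hours run from the start of infusion. The column headers are broken in the text available, so the assignment of columns to days is inferred. Section 6.5 supports it independently.

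**The concern.** With a constant-rate infusion, the highest concentration comes when the infusion stops. A grid that jumps from 3 h to 5 h does not observe it. C1D1 is the only day on which romidepsin is given alone: Section 3.4.3.1 holds Tenalisib to Day 3 of Cycle 1 for this purpose. Section 3.2.1.1 says that PK from C1D1 and C1D8 is needed for the escalation decision.

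If the peak is sampled on C1D8 but not on C1D1, romidepsin Cmax will tend to look higher in combination even if Tenalisib does nothing. The protocol also describes Tenalisib as a CYP3A4 inhibitor (3.4.5.1) and romidepsin as a CYP3A4 substrate (3.4.5.2). A real interaction could push in the same direction, and the artefact could not be told apart from it. With 3-6 patients per cohort, a systematic difference between the grids would not average out.

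**Working it through.** **Step 1: put both days on one clock.** Romidepsin time = Tenalisib time − 1 h.

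| Source | C1D8 times on the romidepsin clock (h) | Against C1D1 (0, 1, 2, 3, 5, 7, 9, 10) |
|---|---|---|
| Sections 6.5 and 6.10 | −1, −0.5, 0, 1, 2, 3, 5, 7, 9, 10 | identical from 0 h |
| Footnote 14 | −1, −0.5, 0, 1, 2, 3, 4, 5, 7, 9, 10 | one extra point, 4 h (end of infusion) |

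**Step 2: model for the missed peak.** One compartment, constant-rate infusion for 4 h, k = ln 2 / half-life. The model and the half-life are both assumptions, so the half-life is ranged from 0.25 to 24 h.

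- During infusion: C(t) ∝ 1 − exp(−kt).
- After infusion: C(t) ∝ (1 − exp(−4k)) · exp(−k(t − 4)).
- Observed share of the true peak on C1D1 = max[C(3), C(5)] / C(4). The other scheduled points are lower.
- Apparent C1D8/C1D1 ratio under footnote 14, with no interaction = the inverse of that share.

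Example, half-life 3 h: k = 0.231, C(3) = 0.500, C(4) = 0.603, C(5) = 0.479. Share = 0.500/0.603 = 0.829; ratio = 1.21.

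Example, half-life 1 h: C(3) = 0.875, C(4) = 0.9375. Share = 0.933; ratio = 1.07.

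| Assumed half-life (h) | Observed C1D1 Cmax / true | Apparent ratio, footnote 14 | Apparent ratio, 6.5/6.10 |
|---|---|---|---|
| 0.25 | 1.00 | 1.00 | 1.00 |
| 0.5 | 0.988 | 1.01 | 1.00 |
| 1 | 0.933 | 1.07 | 1.00 |
| 2 | 0.862 | 1.16 | 1.00 |
| 3 | 0.829 | 1.21 | 1.00 |
| 4 | 0.841 | 1.19 | 1.00 |
| 6 | 0.891 | 1.12 | 1.00 |
| 8 | 0.917 | 1.09 | 1.00 |
| 12 | 0.944 | 1.06 | 1.00 |
| 24 | 0.972 | 1.03 | 1.00 |

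**Step 3: worst case.** The loss is greatest where C(3) = C(5). With x = exp(−k) this is x − x⁵ = 1 − x³, so x ≈ 0.819. The half-life is then about 0.693/0.199 ≈ 3.5 h, the understatement about 18%, and the ratio 1/0.819 ≈ 1.22.

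**Step 4: sampling windows.** I varied the draws (±10 min at 3 h, ±15 min at 4 and 5 h) and the infusion length (3 h 55 min to 4 h 10 min), with the shared draws and infusion length shifted alike on both days. For half-lives of 0.5-12 h the footnote 14 ratio then runs from 1.00 to about 1.28.

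**Step 5: AUC.** Under footnote 14, the extra point also raises the trapezoidal AUC over 0-10 h on C1D8 relative to C1D1, by about 2% to 13% over the same half-lives.

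**Step 6: the post-infusion label.** Read literally, the first C1D1 draw after the pre-infusion sample would fall 5 h from the start. With a 1 h half-life that captures 50% of the peak. Section 6.10 does not support that reading, but the label permits it.

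**The case against.** A reader might infer that the trial will report a false interaction. The documents do not support that, for these reasons:

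- Sections 6.5 and 6.10 give matching grids, and footnote 14 defers to 6.10. The stray 5 may be a typographical error. If 6.10 is trusted to correct the post-infusion label, it can be trusted on the extra time point too.
- Footnote 14 times the C1D8 samples from the Tenalisib dose and names no analyte for the 5 h draw. If that sample is assayed for Tenalisib only, romidepsin Cmax is unaffected.
- No C1D8/C1D1 ratio is planned. Protocol 9.4.4 specifies descriptive summaries by dose, and SAP Section 11 leaves PK to another organisation. The escalation rule is a count of DLTs, and no Cmax threshold is stated.
- The size depends on a half-life that the documents do not give. At either end of the assumed range the effect is small or nil.

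All of this stands, and it makes the false interaction conditional. It does not touch two points. Every C1D1 grid omits the end of infusion, whichever section governs. And the three places disagree in the current text, in a schedule of events that sites may work from. Descriptive summaries of the two days, set side by side, would still carry any difference in sampling.

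**Conclusion.** The point holds in two parts of different strength.

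- **Unconditional on the text:** no C1D1 schedule has a draw at the end of the infusion, so Cmax for romidepsin alone is understated. The size is about 0-18% under a one-compartment model with an assumed half-life of 0.25-24 h.
- **Conditional:** if sites follow footnote 14 and the 5 h sample is assayed for romidepsin, the C1D8/C1D1 Cmax ratio can read from 1.00 to about 1.22 at nominal times with no interaction. If sites follow 6.5 and 6.10, both days miss the peak equally and the ratio is 1.00.

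The post-infusion label in footnote 14 is a separate inconsistency with 6.10. The plan should be corrected because the C1D1 and C1D8 PK data feed the escalation review. The documents show no decision that the error would by itself reverse.

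**What to change.** 1. Reconcile Sections 6.5 and 6.10 and footnote 14 to one romidepsin grid, timed from the start of infusion and identical on C1D1 and C1D8. State the analyte for each sample.
2. Add a draw just before the end of infusion on both days: nominal 4 h, which is Tenalisib 5 h on C1D8. Give it a window that closes before the infusion stops. The ±15 min window in 6.10, with an infusion allowed to end at 3 h 55 min, would let a 4 h 15 min draw fall 20 min after the end.
3. Record actual draw times and infusion start and stop times.
4. In footnote 14, replace post-infusion with from start of infusion.

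The draw should be added, not obtained by moving the 3 h draw to 4 h. On C1D8, romidepsin 3 h is Tenalisib 4 h, so a move would remove that Tenalisib sample and its matched ECG, and would leave romidepsin unsampled between 2 and 4 h.

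Cost: one extra small blood draw per day relative to 6.10 (on C1D1 only, relative to footnote 14), a matched ECG if the ECG grid stays tied to PK, and text edits in three places.

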7 ASSESSMENT OF SAFETY

7.1 Adverse Events

The PI is responsible for collecting and reporting adverse events (see Section 7.1.2). It is Sponsor responsibility to report relevant SAEs to the applicable regulatory body.

7.1.1 Definitions of Adverse Events

Any untoward medical occurrence in a patient or clinical investigation subject administered a pharmaceutical product and which does not necessarily have a causal relationship with this treatment. An adverse event (AE) can therefore be any unfavourable and unintended sign (including an abnormal laboratory finding), symptom, or disease temporally associated with the use of an investigational product, whether or not related to the investigational product.

7.1.2 Recording of Adverse Events

All adverse events of any patient during the course of the trial will be reported in the case report form, and the investigator will give his or her opinion as to the relationship of the adverse event to trial drug treatment (i.e., whether the event is related or unrelated to trial drug administration). If the adverse event is serious, it should be reported immediately to Sponsor. Other untoward events occurring in the framework of a clinical trial are also to be recorded as AEs (i.e., AEs that occur prior to assignment of trial treatment that are related to a protocol-mandated intervention, including invasive procedures such as biopsies, medication washout, or no treatment run-in).

All AEs regardless of seriousness or relationship to Tenalisib/Romidepsin, spanning from the informed consent drug until 30 calendar days after the last dose of study drug, discontinuation or completion of protocol-specific treatment as defined by the protocol for that patient, are to be recorded in the electronic Case Record Form (eCRF).

7.1.3 Handling of Adverse Events

All adverse events resulting in discontinuation from the trial should be followed until resolution or stabilization. Patients must be followed for AEs for 30 calendar days after the last dose of study treatment. All new AEs occurring during this period must be reported and followed until resolution unless, in the opinion of the investigator, the adverse event or laboratory abnormality/ies are not likely to improve because of the underlying disease. In this case, the investigators must record his or her reasoning for this decision in the patient's medical record and as a comment on the eCRF. After 30 days of completion of protocol-specific treatment or discontinuation, only AEs, SAEs, or deaths assessed by the investigator as treatment related are to be reported.

7.2 Adverse Event/Serious Adverse Event Causality Assessment

Causality is assessing the relationship of the trial treatment to the adverse event. For this study, the causality assessment will be categorized as related and not related.

- **Related:** All toxicities should be considered to be related to Tenalisib/Romidepsin unless there is a clear alternative explanation.
- **Not related:** If there is no temporal association, or another etiology has been identified as the cause, or the trial treatment cannot be implicated based upon the current information.

7.3 Serious Adverse Events

7.3.1 Definitions of Serious Adverse Events

The definitions of serious adverse events (SAEs) are given below. The principal investigator is responsible for ensuring that all staff involved in the trial is familiar with the content of this section.

An SAE or reaction is defined as any untoward medical occurrence that: results in death, is immediately life-threatening, requires at least a 24-hour in-patient hospitalization or prolongation of existing hospitalization, results in persistent or significant disability/incapacity, or is a congenital anomaly/birth defect.

The definition of SAE also includes any important medical event. Medical and scientific judgment should be exercised in deciding whether expedited reporting is appropriate in other situations, such as important medical events that may not be immediately life-threatening or result in death or hospitalization, but may jeopardize the patient or may require intervention to prevent one of the other outcomes listed in the previous definition. These should also usually be considered serious. Examples of such events are intensive treatment in an emergency room or at home for allergic bronchospasm; blood dyscrasias or convulsions that do not result in hospitalization; or development of drug dependency or drug abuse. ***Progression of malignancy (including fatal outcomes), if documented by use of appropriate method (for example, as per Lugano classification 2014), should not be reported as a serious adverse event.***

Treatment within or admission to the following facilities is not considered to meet the criteria of “in-patient hospitalization” (although if any other SAE criteria are met, the event must still be treated as an SAE and immediately reported):

- Emergency Department or Emergency Room
- Outpatient or same-day surgery units
- Observation or short-stay in unit or short stay to facilitate PK blood draws
- Rehabilitation facility
- Hospice or skilled nursing facility
- Nursing homes, Custodial care or Respite care facility

Hospitalization during the trial for a pre-planned surgical or medical procedure (one which is planned prior to entry in the trial or planned in advance and not related to the study procedure/drug), does not require reporting as a serious adverse event to the Sponsor.

7.3.2 SAE Reporting by Investigators

It is important to distinguish between “serious” and “severe” adverse events, as the terms are not synonymous. Severity is a measure of intensity; however, an AE of severe intensity need not necessarily be considered serious. For example, nausea which persists for several hours may be considered severe nausea, but may not be considered an SAE. On the other hand, a stroke which results in only a limited degree of disability may be considered only a mild stroke, but would be considered an SAE. Severity and seriousness should be independently assessed when recording AEs on the eCRF and SAEs on the SAE Report Form.

Adverse events classified by the treating investigator as **serious** require expeditious handling and reporting to sponsor in order to comply with regulatory requirements. Serious adverse events may

occur at any time from the signing of the informed consent form through the 30-day follow-up period after the last trial treatment. Sponsor/sponsor representative must be notified of all SAEs, regardless of causality, within 1 day of the first knowledge of the event by the investigator.

To report an SAE, the SAE Report Form should be completed with the necessary information. All SAEs occurring from the signing of consent until 30 calendar days of last trial treatment must be reported to the Sponsor as SAEs on the SAE Report and followed until resolution (with autopsy report if applicable).

Deaths and other SAEs occurring >30 calendar days after last trial treatment that are deemed related to Tenalisib/Romidepsin must be reported as SAEs on the SAE Report within 1 day of first knowledge of the event by the treating physician or research personnel (with an autopsy report if available). Deaths occurring >30 calendar days after last trial treatment and not attributed to trial treatment (e.g., disease progression) need not be reported as SAEs, but simply captured on the appropriate eCRF.

The SAE Report Form should be sent to the sponsor/sponsor representative via fax or e-mail within 24 hours of becoming aware of the event. The detailed SAE reporting process will be reviewed with sites during the site initiation visit as well as provided on the SAE report itself. Transmission of the SAE report should be confirmed by the site personnel submitting the report. Follow-up information for SAEs and information on non-serious AEs that become serious should also be reported to Sponsor as soon as it is available; these reports should be submitted using the SAE Report Form.

Investigators must report SAEs and follow-up information to their responsible IRB/IEC according to the policies of the responsible IRB/IEC.

